1. STUDY OBJECTIVES

1.1 Primary Objectives

Hypothesis 1: FORT-A will result in significantly greater improvements in pain management among PRC Veterans compared to standard PRC care based on the primary outcome measure of self-report disability (Oswestry Disability Index) at both short- (pre- to post-treatment) and long-term (6/12-month) follow-up.

Hypothesis 2: FORT-A will also result in significant improvements on secondary pain management outcomes compared to PRC, including pain coping (intensity/ cognitions), emotional distress (depression, PTSD, anxiety), and objective disability (functional capacity, gait) at short- and long-term follow-up.

Hypothesis 3: We hypothesize that FORT-A will result in significantly lower rates of opioid recidivism compared to standard PRC treatment based on timeline followback interview at 12-months follow-up.

Hypothesis 4: We also hypothesize that FORT-A will result in significantly less opioid recidivism compared to PRC treatment based on secondary measures of opioid medications including Medication Event Monitoring System (MEMS), pill counts, and consultation with prescribing providers/ documentation in the VA Electronic Health Record (CPRS).

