Secondary Hypothesis: FORT-A participants will demonstrate significantly lower rates of opioid recidivism than TAU participants at one-year post-treatment. Opioid and other pain medication use is being assessed using a timeline follow-back interview and MEMS caps (with the timeline follow-back as the primary measure based on its documented reliability and validity; Sobell & Sobell, 1992).

- ***We are currently discussing the value of adding urine tox screens at pre-treatment, post-treatment, and one-year follow-up.*** The study team previously eschewed the use of a urine tox screen for this research endpoint

because of concerns about the validity and sensitivity of urine tox screens for opioid use. However, in consultation with [name] and the VA Opioid Safety Initiative, we have identified certain tests applied to a urine sample that can reliably and validly illuminate opioid use patterns. We are still examining this addition and how we might be able to partner with the VA to add this to our outcome battery (after discussing this with NCCIH more, of course) without additional cost. The VA system has increased implementation of urine tox screens for opioid using Veterans (see <http://www.veterans.senate.gov/imo/media/doc/VA%20Clancy%20Testimony%203.26.20151.pdf>). However, studies in the PRC population using urine tox screening risk high attrition because Veterans may feel mistrusted. Because timeline followback has shown reliability and validity in the past, we have chosen to stay with this method for tracking opioid use and recidivism to opioid use. However, we will have access to electronic medical records (CPRS) to identify new opioid prescriptions in the VA system and [name] and [name] can access the *Prescription Access in Texas* website (see <https://www.texaspatx.com/Tutorial/Doc/PATIFAQs.pdf>), the Texas State prescription monitoring program, to identify opioid prescriptions dispensed outside of the VA. We are able to keep all opioid medication use confidential as part of the research record and hope that this will increase the reliability and validity of reporting.

Tertiary Hypotheses:

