9.2 Sample Size and Randomization

The study is powered to detect a clinically meaningful difference between the two intervention groups on the primary outcome (ODI score) at the 12-month follow-up time period. This endpoint was chosen as it represents the durability of the treatment effect and best reflects the potential utility of the FORT-A program for improving the life of patients. The effect sizes used in the calculation are based on our previous FORT trial, for which treatment effects in the FORT study arm were maintained at the one-year follow-up.

Although Aim 2 changed in September 2015, it is important to note that the study must be powered for Aim 1 for two reasons. First, Aim 1 represents the most immediately relevant clinical endpoint, demonstrating that the FORT-A program is clinically superior to Treatment As Usual in this complex patient population. Second, the PI's previous military FORT study revealed a significant decrease in opioid medication use for program completers (compared to TAU). The resulting data suggest that improved pain management through functional restoration is a likely mechanism opioid medication reduction in military pain populations. Thus, Aim 1 must be met to maximize between-groups differences in Aim 2.

To best assess Aim 2, we have chosen to assess medication (opioid and non-opioid) use on a monthly basis (during follow-up assessments and monthly phone calls) using the TLFB and the MQS. The increased frequency in assessment (each measure will be given 12 times) will provide ample power to detect between-groups difference in opioid recidivism over the 12-month study period. Assuming a sample size of $N = 130$ ($n = 65/\text{group}$), 12 data collection periods (monthly follow-ups for one year), and a statistical significance level of 0.05, the analysis will have power = .80 to detect a clinically meaningful difference between the study groups. For example, if the control group exhibits a recidivism rate of 45% (as suggested in Section 2.1 of this document) and the active treatment group exhibits a recidivism rate of 22.5%, the study will have power = .80.

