9.6 Data Analyses

Data Analysis: To examine our aims and hypotheses we will utilize the generalized linear model, which allows specification of an appropriate distribution for each outcome that can accommodate continuous outcomes (e.g., normal distribution with identity or log link for self-reported disability) and presence/absence outcomes (e.g., binomial with logit link for probability of daily opioid use). We will not stratify our analyses by PTSD or depression, but will account for these variables in our data analysis. Furthermore, we will attend to the influence of missing data on our analyses, and plan on conducting missing values analysis to inform several sensitivity analyses (e.g., LOCF, multiple imputation, etc.) to ensure an intent-to treat principle is observed. Specifically, we will examine the MAR assumption by examining patterns of missingness conditional on baseline assessments, treatment adherence, or other time-varying predictors. Our RCT has one primary endpoint (Oswestry), so both primary and secondary outcomes will be interpreted at a conventional level of statistical significance, $p < 0.05$. To adhere to NIH policy of examining gender and ethnic subgroup analyses, we will add interaction terms (i.e., treatment group x subgroup) for each of our planned analyses. Each analysis is further detailed below:

AIM 1: Assess the efficacy of the FORT-A Program for improved pain management outcomes in (N=130) polymorbid OEF/OIF/OND PRC Veterans with chronic orthopedic pain using a 1:1 randomized clinical trial comparing FORT-A to standard PRC care. To examine our primary hypothesis, we will compare the self-reported disability scores of the two groups at 12-month follow-up while controlling for baseline scores (i.e., an ANCOVA approach). A statistically significant main effect will be interpreted as the groups exhibiting differential change in regards disability. Secondary analyses will use growth curve modeling (mixed effects hierarchical regression with polynomial change parameters) which will model differences in change trajectory over time between the groups across assessment occasions.

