AIM 2: Assess the efficacy of FORT-A for decreasing the rate of opioid medication recidivism compared to standard PRC care in a sample of OEF/OIF/OND polymorbid LBP Veterans. To examine our primary hypothesis, we will compare the rate of opioid medication recidivism between the two groups monthly from baseline to 12-month follow-up. As noted above, 30-40% of TAU participants are expected to meet criteria for opioid recidivism (use of any opioid medication for 3 days or more in the last 30 days at each assessment). A statistically significant main effect will be interpreted as the groups exhibiting differential change in regards disability. Secondary analyses will be conducted using growth curve modeling (i.e., mixed effects hierarchical regression with polynomial change parameters to model differences in the trajectory of opioid use over time between the groups by time).

EXPLORATORY AIM 3: To examine the role of helplessness and perceived burdensomeness in predicting the trajectory of change over time, we will use latent

growth curve modeling. We will first model the trajectory of change in the two primary outcomes as a function of group (Aim 1 and Aim 2). We will then model the trajectories of helplessness and perceived burdensomeness as a function of group. Assuming both associations are observed (i.e., that group status is related to changes in the outcomes and the mediators), we will conduct hierarchical entry of group status and each mediator to examine if group status is still associated with outcome after adjusting for changes in the mediators. This will allow us to assess the role of the mediators in predicting the outcome and the proportion of change trajectory attributed to changes in these mediators.

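### Aim 2 opioid recidivism is tested at 12 months in Hypothesis 3 and 9.1 but as a monthly comparison from baseline in 9.6, and nothing says which one decides

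*Combined protocol and SAP*

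**What the plan says.** - Section 1.1, Hypothesis 3, expects "significantly lower rates of opioid recidivism compared to standard PRC treatment based on timeline followback interview at 12-months follow-up".
- Section 9.1, Secondary Hypothesis, says "FORT-A participants will demonstrate significantly lower rates of opioid recidivism than TAU participants at one-year post-treatment".
- Section 9.6, Aim 2, says "we will compare the rate of opioid medication recidivism between the two groups monthly from baseline to 12-month follow-up". It counts a person as a case after 3 or more days of use in the last 30 days at each assessment, and expects 30–40% of the usual-care arm to meet this. A significant main effect is then to be interpreted as differential change in disability. Growth curves are secondary.
- Section 9.2 describes 12 monthly data collections and power to "detect between-groups difference in opioid recidivism over the 12-month study period". Its example is 45% v 22.5%, 65 per arm, power 0.80.
- The general model sentence in 9.6 gives, as an example of a binary outcome, "binomial with logit link for probability of daily opioid use".
- Section 9.6 also says that primary and secondary outcomes are read at p < 0.05.

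The instrument is settled: Sections 3 and 9.5.2 name the timeline followback interview (TLFB) as the leading opioid measure. For Aim 1, 9.6 names both the time point and the model, an ANCOVA at 12 months.

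**The concern.** Status at the 12-month visit and average monthly status over the year are different quantities. The first asks whether the benefit is present at the end of follow-up; the second asks how much recidivism occurred along the way. If the effect wanes, the second can be clearly positive while the first is null. An analyst who follows 1.1 and 9.1 and one who follows 9.6 would each be following the protocol, yet could report opposite conclusions. If the choice is left until the data are seen, the chance of a false claim of lower recidivism exceeds 5%.

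The decision sentence does not help, because it names the wrong outcome for Aim 2. Section 9.6 also names no model for correlated monthly observations in the main Aim 2 comparison. The stake is a formal efficacy aim, rewritten in Amendment 6 to ask whether veterans can be kept from returning to opioids.

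**Working it through.** **1. The plan's own figure.** Inputs from 9.2: n = 65 per arm, p1 = 0.45, p2 = 0.225, α = 0.05 (taken as two-sided; 9.2 does not say for Aim 2).

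Power = Φ{[|p1 − p2|√n − 1.96√(2p̄q̄)] / √(p1q1 + p2q2)}, with p̄ = 0.3375 and q̄ = 1 − p̄.

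- |p1 − p2|√n = 0.225 × 8.062 = 1.814
- 1.96 × √0.4472 = 1.311
- √(0.2475 + 0.1744) = 0.6495
- Φ(0.503 / 0.6495) = Φ(0.775) = 0.78

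With unpooled variance it is Φ(1.814/0.6495 − 1.96) = 0.80. The stated power therefore reproduces as one proportion per patient, although the text refers to 12 assessments. It does not identify the deciding contrast.

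**2. Do the two stated tests agree when the rates apply at each visit?** This is the 9.6 reading.
- From the documents: 65 per arm, 12 monthly assessments, control rate 30–40% (9.6) or 45% (9.2).
- Assumed: treatment halves the rate, as in the 9.2 example; the rate is constant over months; latent within-person correlation is 0.5, 0.7 or 0.9; no dropout.
- Tests: pooled z-test on month-12 status; t-test on each person's mean of 12 monthly indicators, standing in for a marginal model.
- 6,000 simulated trials per cell.

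| Rates | Correlation | Power, month 12 | Power, monthly | Verdicts differ |
|---|---|---|---|---|
| 30% v 15% | 0.5 / 0.7 / 0.9 | 0.55 / 0.54 / 0.55 | 0.93 / 0.82 / 0.69 | 40% / 33% / 22% |
| 40% v 20% | 0.5 / 0.7 / 0.9 | 0.72 / 0.72 / 0.71 | 0.99 / 0.93 / 0.84 | 27% / 23% / 17% |
| 45% v 22.5% | 0.5 / 0.7 / 0.9 | 0.79 / 0.79 / 0.79 | 0.99 / 0.96 / 0.90 | 21% / 18% / 14% |

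Most disagreements have the monthly test significant and the 12-month test not.

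**3. If 45% v 22.5% means ever in the year.** Monthly entry is 1 − 0.55^(1/12) = 4.9% and 1 − 0.775^(1/12) = 2.1%. Mean episode length is assumed to be 1 to 6 months. Month-12 status is then about 4.5% v 2.1% (1-month episodes) up to 21.5% v 10.2% (6-month episodes). Power is about 0.12–0.41 at month 12 and 0.65–0.84 for the monthly average, and the verdicts differ in about 35–75% of trials.

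**4. If the effect wanes.** Assume control 45% throughout, FORT-A rising from 15% to 40%, and correlation 0.5–0.9. Power is about 0.09 at month 12 and 0.72–0.93 for the monthly average.

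**5. No true difference.** The chance that at least one of the two tests is significant at 0.05 is about 7–9% under the model in step 2 (30–45% in both arms) and about 8–10% under the model in step 3 (40% ever in both arms).

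**The case against.** The best defence is that 9.6 governs. It is the analysis section, it introduces the monthly comparison as the examination of the main Aim 2 hypothesis, and it puts growth curves second. That ranks the monthly comparison above growth curves. It does not rank it above the 12-month comparison, which two other current sections state as the hypothesis.

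A reader might infer stronger versions of the point, which the documents do not support:

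- **A four-way conflict.** Daily opioid use is only an example in a sentence about what the model family can accommodate, and that paragraph defers to the detail below it. It is not a planned fourth test. Section 9.2, with its 12 monthly periods, fits 9.6.
- **A planned ever-in-the-year test.** No section states one. It is an inference from the period wording in 9.2. False-positive figures that count it as a third test run to 10–13% and overstate the problem.
- **Low power at 12 months as the general case.** Values of 0.12–0.41 arise only if 45% v 22.5% is read as ever in the year with short episodes. Section 9.6 describes its rates as holding at each assessment, which gives 0.54–0.79.
- **No decision rule at all.** The sentence about disability repeats the Aim 1 sentence and looks like a copying slip. The outcome compared is named just before it.
- **A licence to pick.** The p < 0.05 statement covers primary and secondary outcomes. It does not authorise choosing among contrasts for one outcome, though it does not prevent it either.

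It is also fair that Sections 3 and 9.1 make Aim 2 secondary and that 9.6 names ODI as the one primary endpoint.

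**Conclusion.** The point holds as a conflict between two stated contrasts: 12-month status (Hypothesis 3 and 9.1) and a main effect on monthly recidivism (9.6). No section says which decides.

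Its size depends on what the stated rates mean. Verdicts differ in about 14–40% of trials on the per-visit reading and about 35–75% on the ever-in-year reading. Using either test at 0.05 gives about 7–10% false positives instead of 5%. These figures rest on assumed correlations, episode lengths and a halving of the rate, with complete follow-up of 65 per arm. The documents give no correlation or episode length. The figures show that disagreement is likely enough to matter; they do not predict this trial.

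This should be corrected, but it does not threaten the trial's primary ODI conclusion.

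**What to change.** Before data lock, name one deciding contrast for Aim 2. One workable choice keeps 9.6: a single treatment effect on the monthly TLFB indicator (3 or more days in 30) over the post-treatment months, from a model that allows for within-person correlation. Name either GEE or mixed logistic regression, since they estimate different odds ratios. Then:

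- reword Hypothesis 3 and the 9.1 Secondary Hypothesis to that contrast;
- report 12-month status as supportive, with a confidence interval;
- replace disability with opioid recidivism in the Aim 2 decision sentence of 9.6;
- as an editorial alignment only, change the daily-use example in the general model sentence to the recidivism indicator.

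If durability at one year is the question that matters most, the sponsor could choose 12-month status instead and reword 9.6. What matters is that one is named.

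The cost is protocol and SAP wording. The monthly TLFB data are already scheduled, so no patients, visits or measures are added. The downside is that one contrast carries Aim 2 and the other becomes supportive.

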The few publications describing the effectiveness of the OSI show a significant drop in the rate of opioid prescription in the VA system, especially for veterans on high doses of opioid medications (Westanmo et al., 2015). A PCORI Topic Brief published in June 2015 provides a comprehensive review of the data on safety and efficacy of opioid medications, and the available data largely show that opioid medications are “weakly” effective in the long-term management of chronic pain and there is very little data describing the best way to discontinue opioid medications, and no good research describing the long-term consequences for pain management and opioid recidivism for those who are discontinued (which mirrors Congressional Testimony by VA Official [name] in 2014 describing a large reduction in opioid prescriptions throughout the VA attributable to OSI. The South Texas Veterans Health Care System, where this study will take place, was recently identified as a top ten performer for OSI outcomes, so STVHCS veterans are increasingly likely to become former opioid users.

Although there is little VA data describing the outcome of opioid prescription tapering or discontinuation in veterans, there is some helpful data offering insight into what could occur. A small-scale study of an Opioid Renewal Clinic in the Philadelphia VA found a recidivism rate of over 40% for veterans who discontinued opioids (with higher rates for those not engaged in an intervention program for high risk opioid abusers; Becker et al., 2009). An older study of Vietnam veterans also found a 40% rate of future opioid use after military discharge among veterans who were “addicted” to opioid medication during active duty service (O’Brien et al., 1980). A rat-model study of opiate withdrawal after chronic opioid treatment found an increased rate of cocaine-seeking behaviors (He & Grasing, 2004).

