9.3 Definition of Populations

For this study, the per-protocol population will include all participants who completed all assessments and interventions with no major protocol deviations (as defined by Gupta, 2011). The primary analysis will be conducted on the Intent-to-Treat (ITT) population that will include all randomized participants who have completed baseline assessments. In the original trial, all FORT completers participated in all assessments, but approximately 20% of Treatment as Usual participants were lost to follow-up. Analysis of baseline data revealed that most missing data were missing at random.

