Study personnel blind to participant randomization can use the VA electronic health record (CPRS) to identify active and new opioid medication prescriptions from providers working in the VA system. Study physicians ([name] and [name]) get free access to the Prescription Access in Texas (PAT) prescription monitoring program to examine any and all Schedule II through V medications given by any provider in the State of Texas. Both CPRS and PAT (which maintains records of medications dispensed to a patient for 365 days) will be accessed at each Veteran's one-year follow-up visit to identify medications prescribed over the one-year study participation period.

Psychosocial Trauma and Emotional Measures will be adjudicated through the STRONG STAR Assessment Core using existing SOP for surveillance and adjudication of these measure. STRONG STAR has implemented this process for military and VA studies serving thousands of study participants across dozens of

studies (see Appendix J).

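### Aim 2 has no primary rule for missing monthly TLFB data, and the prescription records that could inform those months are tied to the one-year visit

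*Combined protocol and SAP*

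**What the plan says.** - **Analysis (9.6).** All aims use a generalized linear model. For Aim 2, "we will compare the rate of opioid medication recidivism between the two groups monthly from baseline to 12-month follow-up". Recidivism means opioid use on 3 or more days in the last 30 at each assessment.
- **Missing data (9.6).** The plan is "conducting missing values analysis to inform several sensitivity analyses", with LOCF and multiple imputation as examples, plus an examination of the missing-at-random assumption. None of this is named as the primary handling for Aim 2.
- **Population (9.3).** The primary analysis is intention-to-treat: all randomised participants with a baseline assessment. Of the original FORT trial, the section says that all FORT completers were assessed but "approximately 20% of Treatment as Usual participants were lost to follow-up", and that most missing data were missing at random.
- **Attrition (9.2).** One pooled figure of at most 30% is given for this trial. The same paragraph, which concerns the ODI, expects some form of imputation for up to 30% of individuals.
- **Retrieval (6.2.5, 9.5.2).** Participants lost to contact are approached once more for a TLFB and other forms. The TLFB calendar covers 30 days.
- **Records (9.5.2, 6.1).** CPRS and PAT are accessed at the one-year visit "to identify medications prescribed over the one-year study participation period". PAT holds 365 days. In the Schedule of Evaluations, PAT appears only in the 12-month column and not in the column for participants lost to contact.
- **Planning rates (9.2).** "if the control group exhibits a recidivism rate of 45"% and "the active treatment group exhibits a recidivism rate of 22.5"%, power is stated as 0.80.

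**The concern.** The Aim 2 question concerns everyone randomised. A generalized linear model fitted to monthly TLFB classifications, with no rule for absent months, uses the months that happen to be observed. That is harmless if a missed interview says nothing about opioid use. It is not harmless if people who return to opioids stop answering, and if this happens more in one arm.

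The safeguards named do not settle the matter. LOCF carries a status of no recidivism forward for anyone lost before relapse. The recontact TLFB recovers one 30-day window from those who agree, not the earlier missed months. CPRS and PAT bear on those months, but no section connects them. Because PAT keeps only 365 days, a late query for someone who missed the visit loses the early months for good.

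At stake is the size and possibly the direction of error in the opioid result. If usual care loses more relapsers, a real FORT-A benefit is diluted. If FORT-A loses more relapsers, its benefit is overstated.

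**Working it through.** **Inputs.** Recidivism 45% against 22.5%, 65 per arm and alpha 0.05 (9.2). Two-sided testing is stated for the ODI and assumed here. A usual-care loss of 20% is borrowed from the original trial (9.3). The relapse rate in missing months, p, is not in the documents and is varied over 55%, 65% and 75%.

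**The plan's own figure.** A single two-proportion comparison with all 65 per arm observed has power 0.781 (pooled variance) or 0.798 (unpooled). The stated 0.80 therefore reproduces, but only with no loss.

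**Available-month bias.** Let L be the share of usual-care person-months missing, with none missing in FORT-A.

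- Observed usual-care rate = (0.45 − L × p) / (1 − L)
- Attenuation = [L / (1 − L)] × (p − 0.45) / 0.225

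| L | p | Observed usual-care rate | Observed difference (points) | Attenuation |
|---|---|---|---|---|
| 20% | 45% | 45.0% | 22.5 | 0% |
| 20% | 55% | 42.5% | 20.0 | 11% |
| 20% | 65% | 40.0% | 17.5 | 22% |
| 20% | 75% | 37.5% | 15.0 | 33% |
| 10% | 55% | 43.9% | 21.4 | 5% |
| 10% | 65% | 42.8% | 20.3 | 10% |
| 10% | 75% | 41.7% | 19.2 | 15% |

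Example: L = 20%, p = 65% gives (0.45 − 0.13) / 0.80 = 0.40, and 0.25 × 0.20 / 0.225 = 22%.

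The 20% rows treat a fifth of usual care as unobserved in every month. If that fifth drops out evenly over the year, about half of their months are seen and L is about 10%.

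**Power in the 20% case.** As a single comparison of 52 against 65, power is 0.74 with no bias and 0.64, 0.54 and 0.43 for p = 55%, 65% and 75%. Section 9.2 relies on 12 repeated assessments, so these figures show the direction and scale of the loss. They do not give the trial's actual power.

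**Lower control rate.** Section 9.6 itself says "30-40% of TAU participants are expected to meet criteria for opioid recidivism". With 40% halved to 20%, L = 20%, and the missing months 10 or 20 points above 40%, attenuation is 0.25 × 0.10 / 0.20 = 12.5% or 0.25 × 0.20 / 0.20 = 25%.

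**Equal loss.** If both arms lose the same share and the lost relapse more by the same number of points, the bias cancels. If they relapse more by the same ratio, it does not: with 30% lost in each arm and a ratio of 1.5 to 2, 22.5 points becomes 19.6 to 17.3.

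**The case against.** The strongest reply is that the plan is silent here, not wrong. A reader might infer that it commits to analysing only months with a completed TLFB. It does not say so. It sets an intention-to-treat population, foresees imputation in the ODI paragraph, lists multiple imputation, collects a Missing Data Assessment partly to help impute, and adds a mixed-model growth curve that can use all observed months. All of that stands. Still, none of it is a stated primary rule for Aim 2.

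A reader might also infer that the plan expects heavier loss in usual care. The 20% figure describes the earlier trial and sets FORT completers against all usual-care participants, so it does not show zero loss among everyone randomised to FORT. The same paragraph calls most of that missingness random. For this trial only the pooled rate is given.

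The link from loss to relapse is thin. The background notes recidivism above 40% in an outside clinic, "with higher rates for those not engaged in an intervention program for high risk opioid abusers", which concerns programme engagement and not missed research interviews. The attrition worry in 9.1 concerns urine screening, and 9.5.2 chose the TLFB partly because it carries less stigma. These passages make informative loss plausible; they do not establish it.

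Nor do the records go unused: Hypothesis 4 names CPRS as a secondary measure of recidivism. They are unused only for missing TLFB months.

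**Conclusion.** The point holds as a specification gap with a cheap remedy. Section 9.6 does not say how a missing TLFB month enters the main Aim 2 analysis, and nothing ensures that CPRS and PAT are read for participants who miss the one-year visit. A reader might conclude that the Aim 2 contrast is biased. The documents do not support that as a certainty, because the bias requires missingness tied to relapse and unequal between arms, or equal loss with a proportional excess.

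Under the planning rates and an assumed 55% to 75% relapse in missing usual-care months, with none missing in FORT-A, attenuation is about 11% to 33% with 20% of usual-care months missing and about 5% to 15% with 10% missing. It is nil when missingness is unrelated to relapse. The larger figures are upper-end scenarios. Aim 2 is secondary, so the main conclusion on the ODI is untouched.

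**What to change.** 1. **Section 9.5.2 and the Schedule of Evaluations.** Query CPRS and PAT at the 12-month date for every randomised participant, within the consent given, whether or not the visit is attended. The date matters because PAT looks back only 365 days.
2. **Section 9.6, main Aim 2 analysis.** Analyse all intention-to-treat participants, with missing TLFB months multiply imputed by arm. Predictors are the observed TLFB months (including the recontact TLFB), baseline variables, and a monthly indicator of any opioid dispensed. Keep the available-month model as supportive.
3. **One sensitivity analysis.** Score a missing month as recidivism when the records show 3 or more days of opioid supply in that month. Leave missing months without such a record to the imputation.

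The cost is plan text, a timed query and some analysis work. The records are already planned, and 9.5.2 says study physicians have free access to PAT. The limits should be stated: dispensing is not use, PAT covers Texas only, and non-prescribed opioids are missed. For these reasons the records serve as an imputation predictor and do not replace the TLFB.
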